### Research Strategy

#### **Significance**

**Autosomal Dominant Polycystic Kidney Disease (ADPKD)** is the most common monogenic and potentially fatal disease, affecting about 600,000 Americans and over 12 million people worldwide. It is characterized by progressive development and enlargement of renal cysts which eventually destroy the normal parenchyma, leading to end-stage renal disease (ESRD) in the majority of afflicted patients. Two genes can cause ADPKD, *PKD1* encoding polycystin 1, located on chromosome 16, and *PKD2* encoding polycystin 2, located on chromosome 4. Most (about 85%) ADPKD families have the more severe disease caused by a mutation in *PKD1*, with an average age at onset of ESRD of 56 years, and only 10-20% have the milder form caused by a mutation in *PKD2*, with an average age at ESRD of 73 years. **However, to date there is only one approved therapy, tolvaptan, which has only modest effects on renal disease progression in adult patients with ADPKD.** Despite progress in basic research in ADPKD, the prognosis of patients has not substantially changed in the last 20 years, emphasizing the need for additional and better treatments.

**Relationship between cyst growth and renal function decline in ADPKD.** Although renal cysts begin in fetal life, renal insufficiency is usually delayed beyond the fourth decade. As cysts enlarge, renal parenchymal integrity is compromised and the efficiency of compensation for a reduced glomerular filtration rate (GFR) decreases. Non-cystic nephrons undergo apoptosis and disappear, leaving behind a kidney extensively replaced by cysts and dense bands of fibrotic material. A decline in GFR in ADPKD reflects extensive structural changes and therefore is a late event.

At this time, the best **early biomarker for ADPKD progression is total kidney volume (TKV) determined by magnetic resonance imaging (MRI).** The Consortium for Radiologic Imaging Studies of Polycystic Kidney Disease (CRISP) has clearly shown that increasing TKV, which reflects renal cyst growth, precedes the decline in GFR. Specifically, a height-adjusted TKV of  $\geq 600$  mL predicted progression to chronic kidney disease (CKD) stage 3 within 8 years with 74% sensitivity and 75% specificity. Moreover, MRI imaging can detect a decrease in TKV induced by the administration of tolvaptan within 8 days. Several recent landmark clinical trials in ADPKD have used percent change in TKV as primary outcome parameter to assess effects of interventions in early ADPKD. The relevance of TKV as a predictor of disease progression is further underscored by the recent Food Drug and Administration (FDA) draft guidance concerning TKV. The draft guidance provides qualification recommendations for use of TKV, measured at baseline, as a prognostic biomarker to select patients with ADPKD at high risk for a progressive decline in renal function (defined as a 30% decline in patient's eGFR) for inclusion in interventional clinical trials. **Overall, these findings suggest that kidney volume is an appropriate and important endpoint for evaluation of interventions in clinical trials of adult patients with ADPKD.**

**ADPKD and Metformin.** Although the exact mechanism of cyst formation in ADPKD is still unclear, cyst enlargement is driven by proliferation of cyst-lining epithelial cells and chloride secretion by these cells into the cyst lumen. In addition, the cyst-lining epithelia produce growth factors and inflammatory cytokines, leading to oxidative stress, interstitial inflammation and fibrosis, and apoptosis of the normal tubules. Key downstream molecules driving cyst expansion are cAMP (stimulates both proliferation and secretion) and mammalian target of rapamycin (mTOR, stimulates proliferation), which is normally repressed by polycystin1. Both cAMP and mTOR activity are increased in human cyst epithelia, whereas AMP-activated protein kinase (AMPK), which antagonizes mTOR, is decreased. AMPK also inhibits the cystic fibrosis transmembrane regulator (CFTR) chloride channel, which is required for chloride secretion into the cysts. **Therefore, drugs that activate AMPK, such as metformin, will decrease both cell proliferation and fluid secretion and thus reduce cyst growth.** Activated AMPK can also antagonize transforming growth factor- $\beta$  and inhibit epithelial-mesenchymal transition, both promoters of tubulointerstitial fibrosis.

The efficacy of metformin in reducing cyst burden and preserving normal parenchyma was confirmed in 2 mouse models of rapidly progressive forms of ADPKD. Daily intraperitoneal metformin injections led to a significant decrease in the histological cystic index compared to vehicle treated cystic control mice. Renal function or survival were not examined in this study. The dose of metformin used in mice extrapolated to a dose of about 1500 mg daily for humans when calculated based on body surface area. Up-regulation of AMPK activity by metformin was also beneficial in a subtotal nephrectomy rat model of CKD. Early continuous treatment with metformin prevented the progressive reduction of GFR and renal blood flow that was observed in control animals. While the control animals developed severe renal fibrosis, this was significantly attenuated in the metformin-treated rats. These experiments suggest a direct renoprotective effect of metformin. In humans, a retrospective cohort study of 13,238 veterans who initiated either metformin or sulfonylurea therapy for type 2 diabetes showed that **over 5 years follow-up, metformin users had a significantly lower risk for renal function decline, ESRD or death**, even after adjustments for multiple time-varying covariates.

**We conducted a retrospective cohort study of ADPKD patients with type 2 diabetes** using the Intermountain Healthcare Enterprise Data Warehouse (integrated healthcare delivery system) between 1/1/2000 and 12/31/2013. We identified 31 subjects treated with metformin only who could be matched for age, sex, race, history of hypertension and coronary artery disease, and baseline renal function to 31 subjects not treated with metformin. The primary outcomes were incident ESRD and all-cause mortality. The baseline MDRD-eGFR in participants receiving and not receiving metformin was  $49 \pm 12$  and  $47 \pm 14$  mL/min/1.73m^2 ( $p=0.70$ ). After a median follow-up of 4.5 years, **incident ESRD occurred in 29% and 16% of those not exposed and exposed to metformin, respectively, with a OR of 2.13 (95% CI 1.10-3.46; p=0.02)**. Deaths occurred in 32% and 26% of those not exposed and exposed to metformin, with a OR of 1.37 (95% CI 0.5-2.47;  $p=0.60$ ). Therefore, metformin therapy may slow progression to ESRD in ADPKD adults with type 2 diabetes compared to other antidiabetic drugs.

**Safety and tolerability of metformin in non-diabetic subjects.** Metformin has been used in women with the polycystic ovary syndrome, with or without diabetes, without significant side effects. Nausea and diarrhea may occur in 10-25% of patients but is usually transient and responds to dose reduction. **Long-term metformin administration to non-diabetic individuals** has been studied in the **Diabetes Prevention Program Outcomes Study (DPPOS)**, in which 924 subjects at risk for the development of type 2 diabetes were given metformin 850 mg twice daily for a median of 10 years. Metformin therapy reduced the development of diabetes while no significant safety issues were identified. However, these were subjects with impaired glucose tolerance; only a small study reported the safe administration of metformin (1000 mg/day) to normal-weight women with polycystic ovary syndrome who had normal glucose tolerance tests. Nothing is known about the tolerability of metformin in non-diabetic ADPKD patients, who often are very health-conscious, slim and engaged in vigorous exercise. Therefore **our primary aim is to determine the feasibility, in terms of safety and tolerability, of prescribing metformin 1000 mg twice a day in ADPKD patients with an eGFR of 50-75 mL/min/1.73m^2. Determining the safety of metformin in CKD stage 3 (eGFR 30-60 mL/min/1.73 m^2) is of particular importance**, because these individuals have usually been excluded from treatment with metformin.

Lactic acidosis as a complication of metformin therapy is rare (a Cochrane analysis of 347 trials and cohort studies in type 2 diabetes found no cases of lactic acidosis in 70,490 patient-years of metformin use), however, people with renal impairment may be at higher risk because metformin is 90% renally excreted. Large observational studies of diabetic patients showed that metformin use was associated with lower cardiovascular mortality particularly if subjects also had stage 3 CKD. Based on these reports several recent publications advocate continued use of metformin in diabetic patients with eGFR 45-60 ml/min/1.73 m^2, while reducing the dose by 50% in those with eGFR 30-44 ml/min/1.73 m^2. The **Kidney Disease Improving Global Outcomes (KDIGO)** conference also reviewed this topic and **concluded that there was little evidence to support the relationship between metformin use and development of lactic acidosis in stable CKD patients.** The **major precipitating factor for lactic acidosis** in persons receiving metformin is an **abrupt loss of tubular secretion** which is a characteristic feature of acute kidney injury due to rapid volume depletion or an intercurrent illness. The work group recommended that the dose of metformin should **only be reduced to a maximum of 1000 mg per day when eGFR falls below 45 ml/min/1.73m^2**, and should be discontinued when eGFR reaches 30 ml/min/1.73m^2. We will follow these dosing recommendations.

**Summary of Significance.** The biomedical significance of the proposed work includes:

- ADPKD is the most common life-threatening genetic disease, resulting in ESRD and premature death in the majority of patients;
- Presently, there is only one approved treatment option to slow progression of ADPKD;
- Metformin has a known safety profile with minimal toxicity after decades of clinical experience in diabetic and non-diabetic subjects;
- Surprisingly little is known regarding the safety, tolerability and efficacy of metformin in adult patients with ADPKD and normal to mildly reduced renal function;
- This study will establish the safety of metformin in people with ADPKD;
- We will explore preliminary signals of efficacy of metformin to reduce cyst growth and renal function decline on the background of adequate blood pressure control.

[figure not shown]
**Innovation.** Metformin has never been studied for the treatment of ADPKD. Therefore this is the first use of a randomized placebo-controlled, double-blind study design to determine the feasibility, in terms of safety and tolerability and potential efficacy of metformin in non-diabetic patients with ADPKD. We will also include subjects with stage 3 CKD who have traditionally been excluded from trials with metformin. In addition, our investigative team will use MRI for assessment of total kidney volume. **Overall, this work has the potential to provide important information that will allow us to launch a larger outcomes study that could shift clinical practice guidelines by establishing a novel, easy to deliver therapy for reducing renal structural and functional progression in patients with ADPKD.**

### **Approach**

**Subjects.** After obtaining their written informed consent, 50 non-diabetic men and women aged 30-60 years with a diagnosis of ADPKD based on Ravine criteria and an eGFR 50-80 mL/min/1.73 m^2 will serve as subjects. (The application and the consent form reference 65 patients to account for screen failures and withdrawals.) Because we want to study the tolerability of metformin by non-diabetic subjects, those with diabetes will be excluded. Estimated GFR will be calculated using the chronic kidney disease-Epidemiology Collaboration (CKD-EPI) prediction equation. Hypertensive subjects will have to be on a stable blood pressure (BP) medication regimen for at least 4 weeks, with BP controlled at  $\leq$  130/80 mmHg. Subjects who are not on BP medication but have BP  $\geq$  130/80 mmHg on at least 3 occasions will be required to have their BP controlled for at least 4 weeks before study entry. The first-line antihypertensive medication will be a renin-angiotensin-system blocking drug. Major inclusion/ exclusion criteria are presented in the table below (Table 1).

Table 1	Inclusion Criteria	Exclusion Criteria
	

• Aged 30-60 years

• Adults with diagnosis of ADPKD by modified Pei-Ravine criteria:

➢ With family history: several cysts per kidney (3 if by sonography, 5 if by computed tomography or magnetic resonance imaging)

➢ Without family history: 10 cysts per kidney (by any radiologic method listed above) and exclusion of other cystic kidney diseases. Conditions to be excluded include: multiple simple renal cysts, renal tubular acidosis, cystic dysplasia of the kidney, multicystic kidney, multiocular cysts of the kidney, medullary cystic kidney and acquired cystic disease of the kidney.

➢ Distribution and number of cysts consistent with the observed level of renal function. -OR-

➢ Diagnosis based on genetic testing (PKD1)

• Estimated GFR (CKD-EPI prediction equation) 50-80 mL/min/1.73m^2

• Controlled blood pressure at <math>\leq</math> 130/80 mmHg on a stable anti-hypertensive regimen for at least 4 weeks

• Free from alcohol dependence or abuse.

• Ability to provide informed consent

• Not currently participating in another interventional trial

	

• Uncontrolled hypertension

• Current smokers or history of smoking in the past 12 months

• Diabetes mellitus

• History of hospitalizations within the last 3 months

• History of severe congestive heart failure (i.e., ejection fraction < 35%)

• History of liver disease (metformin is contraindicated in patients with liver disease due to increased risk of lactic acidosis)

• Active infection or antibiotic therapy

• Additional kidney disease (e.g, AKI) superimposed on ADPKD

• Need for treatment with drugs that may enhance the toxicity of metformin, e.g. lamotrigine, topiramate, zonisamide, carbonic anhydrase inhibitors

• Intolerance of metformin

• Immunosuppressive therapy within the last year

• Contraindication to undergoing MRI

• Females of childbearing age: Not willing to use contraception

• Pregnancy/lactation

• BMI <math>< 21</math> kg/m^2

**Experimental Design (Figure 1).** A 1-year randomized, placebo-controlled, double-blind study with metformin will be conducted (see below for dosing). Subjects will undergo telephone and PKD center screening for inclusion/exclusion criteria during a 1-2 week period. After patients meet inclusion/exclusion criteria they will have an abdominal MRI using an established protocol for determination of TKV and liver volume (see below). Subjects will then be randomly assigned to either metformin (Group 1) or placebo (Group 2) which will ensure a balanced experimental design. Members of the investigative team involved in the acquisition and analysis of key outcomes will be blinded to the treatment status of the subjects.

**Figure 1**

Research participants will undergo the following research sessions:

**(i) Session 1: Screening** measurements: Medical history, physical examination, and blood chemistries for serum/plasma creatinine. Arterial BP will be measured in triplicate while seated at rest using an automated oscillometric machine (Dinamap).

**(ii) Session 2: Baseline measurements:**

- Resting arterial blood pressure as above, complete blood count, and comprehensive metabolic panel including a serum/plasma creatinine to estimate GFR using the CKD-EPI prediction equation
- Total Kidney Volume (TKV) and Liver Volume by MRI
- Urine sample for measurement of urine protein and creatinine to estimate urine protein excretion
- Begin study treatment (metformin or placebo)
- Study participant will be given a glucometer and instructed on how to use it at home
- All participants will have the metformin or placebo provided every 3 months. Participants will be asked to return their medication dispenser for a pill count.
- Blood and urine sample will be stored for future measurement of biomarkers of ADPKD progression.

**(iii) Session 3 (Month 3, 6 and 9):** All subjects will be asked about any adverse effects, intercurrent illnesses or changes of their concomitant medications and will have safety laboratories at 3, 6 and 9 months which will include a basic metabolic panel (i.e., serum/plasma glucose and creatinine) to estimate eGFR using the CKD-EPI equation. Study participants will be required to check their morning fasting blood sugars (BS) daily for the first week of treatment, then twice weekly for the following week, and at any time if they experience a hypoglycemic symptom (i.e., sweating, lightheadedness), and keep a log of their BS values. After each dose change of metformin during the titration period (see below) they will again check their fasting BS daily for one week and then twice weekly for the following week. These results will be reviewed during scheduled telephone interviews. Women will be counseled about contraception during the study. Should a pregnancy occur, women are requested to stop taking study drug immediately and contact the study coordinator.

(iv) **Session 4 (Month 12):** Identical to Session 2, with repeat TKV.

**Rationale for age range 30-60 years.** A narrow range for inclusion age criteria will ensure: (i) that the treatment and placebo group are well balanced; and (ii) exclusion of participants older than 60 years with relatively well preserved kidney function will ensure that only ADPKD patients with more advanced disease will be included in the study. Subjects younger than age 30 years very rarely have decreased renal function.

**Rationale for the metformin dosing:** After randomization subjects will start taking metformin/placebo 500 mg twice daily with meals. The dose will be up-titrated every 2 weeks by 500 mg, until 2000 mg/day (i.e., 1000 mg twice a day) is reached for subjects with eGFR > 45 ml/min/1.73m^2. The metformin dose will be increased every 2 weeks if well tolerated, however dose increases may be delayed if the patient reports significant gastrointestinal or other adverse symptoms. In that case the uptitration schedule will be individualized and dose increases will happen when the patient's symptoms have resolved. Of note, these are the recommended dosing guidelines published by the KDIGO update on diabetic kidney disease. The dose of 2000 mg was chosen because it is generally considered the optimal dose for treatment of diabetes or for polycystic ovary syndrome. This dose is also in an equivalent range to the dose used successfully in the mouse models when extrapolated to humans. If intolerable gastrointestinal side effects occur on a higher dose, the dose will be reduced to the previously tolerated dose.

**Rationale for the placebo arm:** Although direct comparisons of the active treatment group with the placebo group will not be required to determine if the pre-specified benchmarks for the safety and tolerability endpoint are met, there are several reasons to include a placebo group in this pilot study. First, a placebo group is required for Specific Aim 2, which will explore differences in TKV and eGFR between subjects treated with metformin or placebo. Second, if a placebo group were not included the investigators and participants would know that they are receiving metformin, which could influence medical management during the study as well as participant's perception of side effects. Third, the inclusion of a placebo group will provide estimates of the proportions of participants who are classified as failures by the primary endpoint due to factors unrelated to metformin.

**Rationale for the duration of follow-up.** Safety and tolerability signals will show by 12 months and changes in eGFR have been described in ADPKD patients with mild CKD. Changes in TKV due to natural progression of ADPKD can be measured after only 6 months and during treatment with tolvaptan after only one week.

**Safety monitoring.** The investigative team will establish an independent Data Safety Monitoring Board (DSMB) for this study. The DSMB will include experienced nephrologists, biostatisticians and endocrinologists. In general, the anticipated gastrointestinal side effects of metformin therapy can be medically managed through adjustment of medications. If medical management is ineffective, doses of the assigned intervention will be reduced by ½ followed by discontinuation of therapy if the side effect persists. The strategies for monitoring the anticipated adverse events are:

**(i) Symptomatic or Asymptomatic Hypoglycemia (glucose < 60 mg/dL):** Study participants will be instructed on management of hypoglycemia. Once symptoms are resolved the patient will be advised to reduce the dose by 50%. If glucose remains < 60 mg/dL in subsequent measurements despite these changes, the intervention will be discontinued. Continuous monitoring of blood glucose with a glucometer will be undertaken until hypoglycemia is resolved.

**(ii) Estimated GFR < 45 mL/min/1.73m^2:** If eGFR falls below 45 ml/min/1.73m^2 and this is confirmed by a subsequent laboratory test 2 weeks later, metformin will be decreased to 1000 mg daily.

**(iii) Estimated GFR < 30 mL/min/1.73m^2:** If eGFR falls below 30 ml/min/1.73m^2 and this is confirmed by a subsequent laboratory test 2 weeks later, metformin will be stopped, according to the KDIGO and American Diabetes Association recommendations.

**(iv) Intercurrent illness:** If a research participant develops volume depletion or an acute intercurrent illness, the patient will be instructed to stop metformin until the illness has resolved. Lactic acid will be measured if suggested by symptoms or lab results (decreased CO2); if elevated, metformin will be stopped and the patient withdrawn from the study.

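### A 30-60 age range cannot balance the arms or guarantee advanced disease; the exploratory TKV and eGFR comparisons should be adjusted for baseline markers already collected

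*Combined protocol and SAP*

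**What the plan says.** The paragraph on the rationale for the age range (Approach) makes two claims. The first is "A narrow range for inclusion age criteria will ensure: (i) that the treatment and placebo group are well balanced". The second is that excluding people over 60 with fairly preserved function "will ensure that only ADPKD patients with more advanced disease will be included in the study". The Experimental Design paragraph adds: "Subjects will then be randomly assigned to either metformin (Group 1) or placebo (Group 2) which will ensure a balanced experimental design".

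Table 1 sets the limits as "Aged 30-60 years" and "Estimated GFR (CKD-EPI prediction equation) 50-80 mL/min/1.73m" squared, with no TKV or genotype threshold; a *PKD1* test is only an alternative route to the diagnosis. The Summary of Significance places the gap in knowledge in "adult patients with ADPKD and normal to mildly reduced renal function".

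The Significance section recognises that progression varies. *PKD1* families are described "with an average age at onset of ESRD of 56 years", and *PKD2* families have an average of 73. It calls TKV the best early biomarker of progression and reports: "The draft guidance provides qualification recommendations for use of TKV, measured at baseline, as a prognostic biomarker to select patients with ADPKD at high risk". Experimental Design places the MRI before assignment.

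The text describes no stratification, blocking, minimisation or covariate adjustment. For TKV and eGFR change, the statistical section gives power statements based on a two-sided test and no analysis model.

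**The concern.** Eligibility limits restrict who enters. They act identically on both arms and cannot balance them, and 30 years is not a narrow span. Random assignment makes arms comparable on average; it does not guarantee balance in any one trial of 50.

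The claim about advanced disease also fails on the entry criteria. A 59-year-old with an eGFR of 80 qualifies: past the average *PKD1* age at ESRD with function largely kept, so presumably a slow progressor. A 31-year-old with an eGFR of 52 qualifies too, and is presumably a fast one.

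At stake is the precision of the 12-month TKV and eGFR comparisons. They are exploratory, but the protocol gives them as the first reason for having a placebo arm and intends to use the data to size the larger trial. The best available marker is measured in time to be used, and no use of it in allocation or analysis is described.

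**Working it through.** **Inputs from the documents.** N = 50, 25 per group; eGFR change +1 versus -4, a difference of 5, with SD 8; TKV growth 5.5% versus 2.8% per year, a difference of 2.7 points, with no SD; two-sided alpha 0.05 (Power calculation for the exploratory outcomes).

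**Assumptions, not in the documents.** The share of fast progressors, the gap in TKV growth between fast and slow, and the marker-outcome correlation r. Each is shown as a range.

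**1. The plan's own eGFR figure.** SE = 8 × √(2/25) = 2.263. Power = Φ(5/2.263 - 1.96) = Φ(0.250) = 0.60 (t-test 0.58). The stated 80% does not reproduce. That is a separate matter, but 0.60 is the right starting point here. For TKV, 80% power at 25 per arm would need SD = 2.7 / (2.8016 × √(2/25)) = 3.41 points.

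**2. Chance imbalance, binary marker.** With K fast progressors among 50 and arms fixed at 25:25, the number X in one arm is hypergeometric(50, K, 25), and the arms differ by |2X - K|/25.

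| K (assumed) | P(difference ≥ 20 points) |
|---|---|
| 10 | 0.074 |
| 15 | 0.217 |
| 20 | 0.148 |
| 25 | 0.258 |

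The values do not rise smoothly. An odd K allows differences of 4, 12, 20, 28 points, so exactly 20 can occur; an even K allows 0, 8, 16, 24, so 20 or more means 24 or more.

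**3. Chance imbalance, continuous marker.** The standardised difference has SD √(2/25) = 0.283. P(|difference| ≥ 0.4) = 2 × [1 - Φ(0.4/0.283)] = 0.16. This needs no assumed share.

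**4. Effect on one estimate.**
- eGFR: shift = r × 0.4 × 8. For r = 0.3 this is 0.96 and for r = 0.5 it is 1.6, or 19% and 32% of the planned 5. Against the SE of 2.263 these are 0.42 and 0.71 SE.
- TKV: a 20-point imbalance with a gap of 2 or 4 points per year shifts the contrast by 0.4 or 0.8, or 15% and 30% of 2.7. With the implied SD of 3.41, SE = 3.41 × √(2/25) = 0.96, so both are below one SE.

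**5. What adjustment recovers.** The residual SD becomes 8 × √(1 - r²).

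| r (assumed) | Residual SD | eGFR power, 25 per arm |
|---|---|---|
| 0 | 8.00 | 0.60 |
| 0.3 | 7.63 | 0.64 |
| 0.4 | 7.33 | 0.67 |
| 0.5 | 6.93 | 0.72 |

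These are normal approximations and ignore the few degrees of freedom spent on covariates.

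**The case against.** The best defence is that participants are randomised. The contrast is unbiased in expectation, and chance imbalance in a prognostic factor is part of the variance that an ordinary confidence interval already covers. That stands. A reader might infer that mixing fast and slow progressors biases the trial or could manufacture a drug effect; the documents support only lost precision and a less reliable single estimate.

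The outcomes concerned are labelled exploratory, and the protocol admits limited power for them. The tolerability benchmarks are judged within the metformin arm and need no comparison with placebo. That also stands: a reader should not carry this point over to the primary conclusion.

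A reader might also infer larger distortions from a wider fast-slow gap. A 6-point gap with a 50:50 mix would give one binary marker a variance of 0.25 × 36 = 9, about 77% of the 3.41² = 11.6 implied by the plan's own TKV power, which is not credible on the plan's terms. Nor do the documents support fearing badly unequal arm sizes: they plan 25 per group, and the balance promised in Experimental Design may simply mean equal numbers. The allocation method is nevertheless unstated.

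Finally, capping age at 60 does exclude some of the mildest disease, so that rationale points the right way. It does not leave only advanced disease.

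**Conclusion.** The point holds as a correction of wording plus an inexpensive gain in precision. The age range does not ensure balance or advanced disease, and the entry criteria admit mixed progression rates. A noticeable imbalance is an ordinary possibility at this size: about 7% to 26% for a 20-point difference in fast progressors, and 16% for a standardised difference of 0.4. Adjustment would lift eGFR power from about 0.60 to between 0.64 and 0.72.

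The 7% to 26% rests on assumed counts of 10 to 25 fast progressors in 50, and the power gain on an assumed correlation of 0.3 to 0.5. The 16% depends only on 25 per arm and a roughly normal marker difference. That no marker is used means none is described in the text; Figure 1 was not seen.

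**What to change.** 1. **Sample Size Calculations and Statistical Analysis, and the exploratory power paragraph:** pre-specify that the 12-month TKV and eGFR change comparisons are made by ANCOVA, adjusted for baseline TKV (log-transformed or height-adjusted), baseline eGFR and age.
2. **Rationale for age range:** delete the claims that the range ensures balanced arms and only advanced disease, and describe the sample as mixed in progression rate.
3. **Experimental Design:** replace the promise of a balanced design with permuted-block 1:1 allocation, which delivers the planned 25 per group.

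Stratifying allocation by one baseline marker is optional. If TKV is chosen, the scan must be read before assignment; adjustment alone avoids that.

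Cost: three covariates take residual degrees of freedom from 48 (50 - 2) to 45 (50 - 5), with a little more analysis work. All three are already collected. No extra participants or visits are needed, and the co-primary endpoints do not change.

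### Study drug may restart after an acute illness with no post-illness creatinine or eGFR required, so the plan's own dose limits at eGFR 45 and 30 cannot be applied at that point

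*Combined protocol and SAP*

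**What the plan says.** Approach, Safety monitoring, item (iv) covers volume depletion and acute illness: "the patient will be instructed to stop metformin until the illness has resolved". The only test it names is conditional: "Lactic acid will be measured if suggested by symptoms or lab results", with a decreased CO2 given as the laboratory trigger. An elevated lactic acid means stopping drug and withdrawal.

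Items (ii) and (iii) hold the renal dose rules. An eGFR below 45 leads to a reduction only once "confirmed by a subsequent laboratory test 2 weeks later, metformin will be decreased to 1000 mg daily". An eGFR below 30 leads to a stop only once "confirmed by a subsequent laboratory test 2 weeks later, metformin will be stopped". Neither item refers to an illness hold.

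The Significance section names a sudden loss of tubular secretion as the main precipitant of lactic acidosis on metformin, "which is a characteristic feature of acute kidney injury due to rapid volume depletion or an intercurrent illness". It adopts the KDIGO dosing advice: at most 1000 mg/day below eGFR 45, and discontinuation at 30. It also gives reassurance. The systematic review it cites "found no cases of lactic acidosis in 70,490 patient-years of metformin use", and the KDIGO group concluded that "there was little evidence to support the relationship between metformin use and development of lactic acidosis in stable CKD patients". Between these it cautions that "people with renal impairment may be at higher risk because metformin is 90% renally excreted".

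Creatinine and eGFR are required at baseline and Months 3, 6, 9 and 12 (Session 3, Session 4, and the eGFR outcome under Outcome Measures). The full dose is 2000 mg/day, and entry eGFR is 50 to 80.

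**The concern.** The events that trigger the hold are those the plan itself associates with acute kidney injury and, through it, with lactic acidosis. Stopping drug is right. The weak step is restart, which depends on the illness having resolved. Symptoms can settle before renal function does, and the text does not say which of the two counts.

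Other safety rules in the plan are more explicit. The hypoglycaemia rule gives a threshold, a dose after recovery and a stopping condition. The pregnancy instruction tells the participant to stop and contact the coordinator. The illness rule gives no renal threshold, restart dose or contact step.

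What is at stake is whether the 45 and 30 limits can operate when they are most likely to be needed. No benchmark, power figure or endpoint definition depends on this.

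**Working it through.** The plan states no figure to reproduce. The check is a reading of the relevant sections plus simple arithmetic.

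**Is a renal check required elsewhere?** The sections on significance, eligibility, sessions, dosing, safety monitoring, outcomes and analysis contain no required creatinine or eGFR after an illness hold and no restart dose. The dosing rationale covers initial titration and gastrointestinal intolerance. The exclusion for superimposed kidney disease applies at entry. The question about intercurrent illness at Months 3, 6 and 9 may come after the participant has already restarted.

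**Time to the next required eGFR.** Four intervals per year: 365/4 = 91.25 days = 13.0 weeks at most. If restarts are spread evenly (assumption), the mean is 45.6 days = 6.5 weeks. The previous value can be equally old. Adding the two-week confirmation gives 13.0 + 2 = 15.0 weeks at most, and 6.5 + 2 = 8.5 weeks on average, before items (ii) or (iii) change a dose. These are properties of the general laboratory schedule and apply to a fall in eGFR from any cause. They bound how long a fall could go unseen by required tests; they do not measure harm.

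**Distance to the limits.**

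| Entry eGFR | Fall to 45 | Fall to 30 |
|---|---|---|
| 50 | 5/50 = 10% | 20/50 = 40% |
| 80 | 35/80 = 44% | 50/80 = 62.5% |

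If the full dose is resumed (assumption, since no restart dose is given), 2000/1000 = 2 times the maximum below 45. Below 30 no drug is allowed.

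**Background rate, for scale only.** Zero events in 70,490 patient-years gives a one-sided 95% upper bound of -ln(0.05)/70,490 = 2.996/70,490 = 4.25 per 100,000 patient-years. For 25 metformin participants over one year: 25 × 0.0000425 = 0.0011 expected cases; at ten times that risk (assumption), 0.011. The source population has type 2 diabetes and does not represent restart after illness in ADPKD.

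**Effect of a restart rule on the co-primary endpoints.** Take a metformin participant who restarts after the Month 9 panel with eGFR persistently below 30. The next required eGFR is Month 12, and its confirmation falls after the 12-month period. Item (iii) therefore does not stop drug during treatment, and the participant may count as a success. Under a restart check, drug would stay on hold and the participant would count as a failure, taking the full-dose credit in Outcome Measures not to extend to a stop. The window is 3/12 = 25% of follow-up, not just the last two weeks. A participant still awaiting a restart panel at Month 12 could also count as a failure. Each such case moves a proportion by 1/25 = 4 percentage points. The analysis section counts reductions for adverse effects that would have followed had the study gone on, so some of these cases may be failures already.

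**The case against.** The strongest counter-argument is that the plan already holds drug in the right circumstances and expects some laboratory work. A CO2 result ordinarily comes on the same basic metabolic panel as creatinine. The instruction to the patient presumes someone at the site giving it. Where the illness is itself volume depletion or kidney injury, a clinician would naturally read resolution as including renal recovery. All of this is fair, and it makes an unsafe restart less likely. None of it makes the test a requirement.

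Second, items (ii) and (iii) act only on confirmed values. Acting on a single restart eGFR is therefore a new rule and not plain adherence to existing ones. This stands, and the amendment should say so. The Significance section does state the 45 and 30 limits without a confirmation step, which is why they are a reasonable interim guide.

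A reader might infer more than the documents support:

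- That eGFR would be unknown at restart. An earlier scheduled value exists; what is missing is a required current one.
- That participants will resume 2000 mg/day. The text permits this but does not direct it.
- That 13 or 15 weeks is time spent at risk. That would need renal loss to persist throughout, and no rate of illness or persistent loss is given.
- That lactic acidosis should be expected here. The plan's own figures point to a rare event, and none may occur.

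Finally, the recruitment section mentions a human subject section that is not among the supplied text and may contain restart procedures.

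**Conclusion.** The point holds in this form: as written, item (iv) permits restart after volume depletion or acute illness without a post-illness creatinine or eGFR, so a participant with persisting renal loss could resume a dose above the limits the plan adopts. The margin is narrowest at the lower end of entry eGFR, where a 10% fall suffices. The size of the clinical risk cannot be derived from the documents, and no event count is claimed. The case rests on making the plan's own limits workable at low cost, and it is graded a cheap improvement. It depends on three things: the quarterly laboratory schedule being the only required testing, resumption at the prior dose being possible, and the supplied text being complete on this subject.

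**What to change.** Amend item (iv). After a hold for volume depletion, vomiting or diarrhoea, febrile or systemic illness, or hospitalisation, the participant contacts the site. A basic metabolic panel with creatinine/eGFR and CO2 is obtained before study drug restarts, in either arm so that blinding is kept. If eGFR is below 45, restart at no more than 1000 mg daily (or matching placebo); if below 30, keep drug on hold. The two-week repeat under items (ii) and (iii) then decides whether the reduction or stop continues. A decreased CO2 leads to the lactic acid test already in item (iv).

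State two things explicitly: that this is an interim restart rule acting on a single value, and that an interim reduction below 45 counts as full dose for the co-primary endpoints. The second is needed because the existing credit refers back to the confirmed rule.

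The cost is one or two sentences, one unscheduled draw and a short restart delay per qualifying hold, plus a repeat draw if eGFR is below 45. At 0.05 to 1 qualifying hold per participant (assumption), 50 participants need about 3 (50 × 0.05 = 2.5) to 50 restart draws, against 50 × 4 = 200 scheduled post-baseline panels. Repeats are extra. The sponsor should also accept, or address in the endpoint rules, the occasional late hold that becomes a co-primary failure.
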